No alert recommending a statin will be displayed/available to the provider. The system will record eligibility through triggering a "silent" alert, which is not displayed to the clinician and exists solely for data collection purposes.

PI: [name], MS

[figure not shown]

Figure 1: Schematic procedure of arm assignment and enrollment.

Both the interruptive and the non-interruptive alerts will have the same format; only the manner in which it is displayed will differ. The reminder will alert clinicians that a statin is recommended for the patient and list the reasons the statin is indicated. It will give the clinicians a defaulted option for statin prescription as well as alternatives. If the clinician accepts the alert, an order for a statin will be placed in their "shopping cart" for convenience, and the order can be signed to prescribe the medication. If the clinician does not wish to prescribe a statin from the reminder, they can choose an acknowledgement reason.

Endpoints

Primary Endpoint

The primary outcome will be a binary outcome of statin prescription placed within 24 hours after enrollment BPA firing (interruptive, non-interruptive, or no reminder) (Yes/No).

Secondary Endpoints

This trial has two secondary outcomes:

- 1. A binary outcome of statin prescription placed within 12 months after enrollment BPA firing (Yes/No)
- 2. The patient's first LDL-C level measured during the follow-up between 30 days and 12 months since the enrollment visit.

PI: [name], MS

Exploratory Endpoints

- 1. A binary outcome of any non-statin lipid lowering agent prescription placed within 12 months after enrollment BPA firing (ezetimibe, PCSK9 inhibitor, or bempedoic acid) (Yes/No)
- 2. A binary outcome of any statin prescription filled within 12 months of enrollment BPA firing (Yes/No)
- 3. A binary outcome of new ASCVD event within 12 months of enrollment BPA firing (Yes/No)
- 4. Time from enrollment BPA firing to statin prescription

Statistical Approach

Target Population

The target population of the estimand will be the principal stratum that includes all participants meeting the above inclusion/exclusion criteria, for whom the randomization allocated by the EHR embedded tool is executed.

Analysis Dataset

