Description of the endpoints:

All the endpoints will be summarized overall and by intervention arm.

Primary Analysis

General approach:

All primary analyses will be performed without covariate adjustment as the study interest lies in estimating the overall intervention effects observed in a diverse patient population in their usual clinical settings. To account for potential imbalance in covariate distribution across arms, secondary analyses will be performed with *a priori* selected covariate adjustment. All analysis results will be reported with point estimates and 95% confidence intervals (CIs). No adjustments for multiplicity will be made.

Analysis of the primary endpoint:

Statin prescription within 24 hours of enrollment BPA firing will be compared between intervention arms using a logistic regression with indicator variables for intervention arms.

Analysis of secondary endpoints:

Statin prescription placed within 12 months after enrollment BPA firing will be analyzed using a logistic regression. For the first LDL-C level measured during the follow-up, a linear regression analysis will be performed with intervention arm indicator variables. If the distribution of LDL-C levels is highly skewed, an ordinal logistic regression analysis will be used in place of a linear regression.

Analysis of the exploratory endpoints:

A logistic regression will be performed to compare the binary outcomes between intervention arms. Time from enrollment BPA firing to statin prescription will be compared between

PI: [name], MS

intervention arms using a Cox proportional hazard model and the differences in the outcome between arms will be visualized using Kaplan-Meier curve.

Secondary Analysis

The covariate adjusted analysis will be performed for the primary and the secondary outcomes using the same regression analysis methods with adjustment of the following covariates.

Covariates for the analysis of statin prescription (the primary endpoint and a secondary endpoint):

Patient age, sex, Charlson Comorbidity Index, type of patient statin therapy recommended to provider, baseline LDL-C level, ASCVD disease, diabetes, chronic kidney disease, prior statin prescription, visit type (in person or telemedicine), and provider role.

Covariates for the analysis of the first LDL-C level measured during the follow-up:

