Patient age, sex, Charlson Comorbidity Index, type of patient statin therapy recommended to provider, baseline LDL-C level, ASCVD disease, diabetes, chronic kidney disease, prior statin prescription, visit type (in person or telemedicine), provider role, and time from enrollment to follow-up LDL-C level measurement.

Population-Level Summaries

Odds ratios (ORs) will be used for the analysis of binary (and ordinal) outcomes. For the analysis of the first LDL-C level measured during the follow-up, the estimates of mean differences in LDL-C levels, comparing interruptive reminder vs. no reminder arms, non-interruptive reminder vs. no reminder arms, and interruptive reminder vs. non-interruptive reminder arms will be used if a linear regress model is used. Hazard ratio (HR) will be used for the analysis of time to statin prescription.

Handling Missing Data

We do not expect missingness in our primary outcome and a secondary outcome of statin prescription within 12 months after BPA firing. Some missingness is expected for the first LDL-C level measured during the follow-up. For these missing outcomes, if a prior LDL-C level is available, the outcome will be imputed using the last known LDL-C level prior to the follow-up period; otherwise, the patient will be excluded in this analysis. For the exploratory outcomes, a complete case analysis will be performed without imputing the missing outcomes.

Missing covariates are not expected, or to be small percentage if occurs, which will be imputed using a single imputation. If missing data are substantial, multiple imputation will be used to handle missing covariates.

Intercurrent Events

To handle intercurrent event due to death or switching providers to other institutions, a whilealive strategy will be used.

Differential Treatment Effects

We will explore differential treatment effects for the primary endpoint only. Differential treatment effects will be explored by examining the interaction between the intervention arm

PI: [name], MS

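### The adjusted LDL-C model includes time to the follow-up test, a post-randomization covariate that can distort the arm effect and is undefined for carried-forward values

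*SAP*

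**What the plan says.** The protocol (12.0, Secondary Analysis) promises covariate-adjusted analyses and leaves the covariates to the SAP.

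- **Endpoint.** SAP, Secondary Endpoints: "The patient's first LDL-C level measured during the follow-up between 30 days and 12 months since the enrollment visit". Neither document fixes a date for this test.
- **Main analysis.** SAP, Primary Analysis, General approach: "All primary analyses will be performed without covariate adjustment". The main LDL-C comparison is thus a regression on arm indicators alone.
- **Purpose of adjustment.** Same paragraph: "To account for potential imbalance in covariate distribution across arms, secondary analyses will be performed", using covariates chosen in advance.
- **Adjusted analysis.** SAP, Secondary Analysis: "The covariate adjusted analysis will be performed for the primary and the secondary outcomes using the same regression analysis methods". Two covariate lists follow, one for statin prescription and one for LDL-C. They match except that the LDL-C list ends with "time from enrollment to follow-up LDL-C level measurement". Neither document gives a reason for the extra item.
- **Missing LDL-C.** SAP, Handling Missing Data: where an earlier value exists, "the outcome will be imputed using the last known LDL-C level prior to the follow-up period". Under Analysis Dataset, only patients still without an outcome after this step are left out. The same missing-data section expects few or no missing covariates, and plans single imputation, or multiple imputation if the gaps are substantial.

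**The concern.** Every other covariate on the LDL-C list describes the patient, provider or visit at enrollment. Time to the follow-up test does not. It comes about after assignment, in an unblinded trial where routine care decides when lipids are rechecked. If a clinician who starts a statin tends to recheck sooner, test time becomes a partial marker of having started one. Holding it fixed then compares patients across arms who are alike on a consequence of the reminder, and part of the reminder's effect on LDL-C can drop out of the arm coefficient.

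A difference between arms in test timing could therefore be a result of the reminder, and adjusting it away is not a correction for imbalance. The SAP would still report the coefficient as the mean difference between arms.

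There is also a practical gap. A patient whose outcome is carried forward had no LDL-C test in the follow-up window, so this covariate has no value for that patient.

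**Working it through.** **The plan's own figure.** The only sample-size figure is for 24-hour prescribing. For 3% against 6%, two-sided 0.05, 90% power, pooled variance (mean rate 0.045):

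n = [1.960·√(2·0.045·0.955) + 1.282·√(0.03·0.97 + 0.06·0.94)]² / 0.03² = 1,001.4, so 1,002 per arm and 3,006 in total.

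This matches the SAP, and the present point does not change it. The documents give no LDL-C effect, LDL-C standard deviation or test timing, so what follows is illustration.

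**Assumed inputs (not in the documents).** A statin lowers LDL-C by 40 mg/dL; test-time SD 80 days within a window of 30 to 365 days; baseline LDL-C SD 30; residual SD about 20. The prescribing rates 3% and 6% are the SAP's. The pair 10% and 30% at 12 months is a deliberately wide contrast that neither document projects.

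**Formula.** Suppose a new statin brings the test forward by k days and timing has no other link to LDL-C. Let v be the average over the two arms of p(1−p). In a linear model with arm and test time, the share of the arm effect that is lost is

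k²v / (80² + k²v).

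For 3% and 6%, v = (0.0291 + 0.0564)/2 = 0.04275, and the full effect is 0.03 × 40 = 1.2 mg/dL. For 10% and 30%, v = (0.09 + 0.21)/2 = 0.15, and the full effect is 0.20 × 40 = 8 mg/dL.

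| Rates | Days earlier (k) | k²v | Loss, formula | Loss, simulated | Simulated, plus an unmeasured cause of earlier tests and lower LDL-C |
|---|---|---|---|---|---|
| 3% vs 6% | 0 | 0 | 0% | 0% | 0.1% |
| 3% vs 6% | 30 | 38.5 | 0.6% | 0.6% | 2.1% |
| 3% vs 6% | 60 | 153.9 | 2.3% | 2.1% | 5.6% |
| 3% vs 6% | 100 | 427.5 | 6.3% | 5.7% | 10.4% |
| 10% vs 30% | 30 | 135 | 2.1% | 2.1% | 3.5% |
| 10% vs 30% | 60 | 540 | 7.8% | 7.6% | 9.9% |
| 10% vs 30% | 100 | 1,500 | 19.0% | 18.1% | 20.9% |

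The simulation truncates test times at 30 and 365 days, so it need not match the formula exactly.

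**Direction.** If the unmeasured cause instead goes with earlier tests and *higher* LDL-C, the adjusted effect at 3% vs 6% is enlarged by 0.5% to 4.2%. At 10% vs 30% the change runs from 1.3% enlargement to 11.1% shrinkage.

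**A more explicit recheck mechanism.** Assume that 80% of starters are rechecked 6 to 14 weeks after starting, that 60% of patients have a background test spread over days 30 to 365, and that a further 10 to 20% start within 12 months. Only measured patients are analysed. At 3% vs 6% the arm coefficient without and with test time was −1.60 and −1.50, −0.83 and −0.73, −0.93 and −0.85, and −2.36 and −2.26 mg/dL. The losses are 0.10/1.60 = 6%, 0.10/0.83 = 12%, 0.08/0.93 = 9% and 0.10/2.36 = 4%. With 3% vs 15% at 24 hours and 10% later starts it moved from −5.92 to −5.21 (0.71/5.92 = 12%). With no statin-triggered recheck there was essentially no change.

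**Against sampling error.** With a residual SD of 22, the standard error of an arm difference is 22·√(2/1000) = 0.98 mg/dL at 1,000 per arm and 22·√(2/2000) = 0.70 at 2,000. A shift of 0.10 is 0.10 and 0.14 standard errors respectively.

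**Undefined values.** This part needs no assumption. The SAP keeps carried-forward patients in the LDL-C analysis, and they have no follow-up test. Fitting the model as listed means either imputing a time for a test that did not take place or dropping patients whom the analysis-set rule retains. The SAP expects missing LDL-C outcomes but little or no missing covariate data, and those expectations conflict for this covariate.

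**The case against.** The strongest reply is that nothing in the documents says a new statin leads to an earlier test, and no timing data by arm are given. Without that link the bias is zero in these models. With a modest 30-day shift at 3% vs 6% it is 0.6%, or about 2% with an unmeasured shared cause. This stands, and the distortion is a possibility rather than a finding. The 80% recheck rate is likewise an assumption, and every simulated scenario that used it was bound to show some loss.

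Second, the shift at the design rates is too small to matter for inference. At a tenth of a standard error, a nominal 95% interval would still cover about 94.9% of the time. This also stands. Losses near 20% needed both 10% vs 30% prescribing and tests 100 days earlier. For non-interruptive against no reminder, the protocol hypothesizes no effect on 24-hour prescribing, so little distortion would be expected there.

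Third, with a window of eleven months some interest in timing is reasonable. That supports a timing-adjusted sensitivity analysis, but it does not make timing a covariate for correcting imbalance.

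A reader might infer that the trial's LDL-C result is biased, or that the adjustment is certain to remove part of the effect. The documents support neither reading: the main LDL-C analysis is unadjusted, and both the presence and the direction of any distortion depend on behaviour they do not describe. None of these replies answers the missing test time for carried-forward patients.

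**Conclusion.** The point holds in limited form. The secondary adjusted LDL-C model conditions on a variable fixed after randomization, which does not fit the SAP's own reason for adjusting and leaves the arm coefficient without an assured reading as the total effect of the reminder. If statin starts bring tests forward, attenuation is the most likely result, though slight enlargement is possible.

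Under the assumed LDL-C and timing inputs, the shift at 3% vs 6% is about 0.1 mg/dL, or 0 to 12% of the effect. It grows with the difference in 12-month prescribing. In the most extreme illustration (10% vs 30%, tests 100 days earlier) it is about 1.5 mg/dL (8.00 to 6.55), which exceeds the standard error.

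The case for change rests on validity and on the undefined values more than on size. The unadjusted LDL-C comparison, the 24-hour primary endpoint and the 12-month prescribing endpoint are untouched.

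**What to change.** In the SAP's covariate list for the follow-up LDL-C analysis, delete time from enrollment to the test and keep the remaining, baseline covariates. Report by arm, descriptively, the timing of the first follow-up LDL-C and the share of patients tested. If a timing-adjusted model is wanted, define it in advance as a labelled sensitivity analysis restricted to patients with a measured follow-up value, and state that its coefficient is not the total effect of assignment.

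The cost is one deleted phrase and a short descriptive table. The drawback is that LDL-C variance due to timing is no longer removed from the adjusted model, so some precision may be lost. The sample size of 3,006 does not change.

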At the core of this study is the imperative to educate providers and promote guideline-concordant patient care. This study necessitates accessing PHI in an identifiable form to ensure that both the interruptive and non-interruptive educational reminders offer appropriate, accurate, and patient-specific guidance. Accessing PHI is also essential for capturing clinical outcomes relevant to the provision of care. All outcome measures assessing changes in provider behavior and resulting impacts, such as statin prescription status and post-intervention LDL-C, are abstracted from the EMR and linked to identifiers. Consequently, the practical execution of the study is dependent on the use of identifiable PHI.

Study Protocol. Version August 9, 2024

Full Study Title: Interruptive versus Non-Interruptive Reminders for Statin Therapy in Primary Care (INIRSHA-PC). A Randomized Trial.

Primary Investigator: [name], MS

Because the study presents minimal risk, would not adversely affect the welfare or privacy rights of the participants, and consent to perform the trial within the primary care clinician space has been received, a waiver of informed consent will be requested.

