## 7.2 Alert format

An example of an alert is shown in Figure 2. The alert education information is customized to the provider based on their patient's clinical characteristics such as 1) the specific reasons that the patient is eligible for a statin (for example, ASCVD risk score or other diagnoses), 2) whether a moderate or high-intensity statin is recommended, 3) whether the patient has liver disease, and 4) whether the patient may have familial hypercholesterolemia based on their cholesterol level. The alert also displays liver testing results for the patient and provides options for statin medications to prescribe. One statin prescription is defaulted, such that if the provider accepts the reminder, the statin medication will be prepared for signing. The clinician also has the opportunity to choose a different statin or a referral to a specialist such as a lipid or gastroenterology specialist. If the clinician does not wish to prescribe a statin at this time, they may select an "acknowledge reason" which specifies the reason for declining statin prescription. The alert also has a feedback link where the clinician can provide feedback about the alert.

The text and information displayed in the alert will remain identical whether the provider receives the interruptive reminder or the non-interruptive alert. The only way that the alert will differ between interruptive and non-interruptive arms is the place in the workflow in which the clinician encounters it.

Study Protocol. Version August 9, 2024  
Full Study Title: Interruptive versus Non-Interruptive Reminders for Statin Therapy in Primary Care (INIRSHA-PC). A Randomized Trial.  
Primary Investigator: [name], MS

! Statin therapy recommended

Patient is recommended to be on **moderate intensity statin** for the following reason(s):  
• Patient may have an ASCVD risk score  $\geq 10$

Here are the patient's most recent LFTs:

Component	Value	Date
ALT	22	05/16/2022
AST	27	05/16/2022
ALKPHOS	97	05/16/2022
BILITOTAL	0.7	05/16/2022

If the patient has a history of statin intolerance and you're unsure of whether to start a statin, consider reviewing [UpToDate](#) or placing a referral to the lipid clinic.

Order	Do Not Order
Order	Atorvastatin (LIPITOR) tablet 20 mg
Order	Rosuvastatin (CRESTOR) tablet 10 mg
Order	Ambulatory referral to lipid clinic

Acknowledge Reason

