
With the widespread use of EHRs and the implementation of reminders, the decision to build an alert as interruptive or non-interruptive is an important one which must balance potential alert fatigue with potential positive effects on adherence to clinical guidelines which improve quality of care for patients. Rigorous studies are needed to gather evidence to help clinical informaticians when making decisions about the design of CDS interventions. Findings from such studies would have implications for the thousands of alerts displayed to clinicians each year. To address this knowledge gap, we will conduct a prospective, randomized trial of reminders delivered to clinicians seeing patients in primary care clinics, comparing interruptive vs. non-interruptive reminders in outcomes of statin prescriptions.

Population and Design Considerations

Study Population:

Adult patients (age \geq 18 and < 75) who are treated by primary care providers at Vanderbilt University Medical Center and eligible for statin therapy but not currently on a statin are potentially eligible for this study. If a patient presents to a VUMC primary care clinic and meets the below inclusion and exclusion criteria, the patient will be enrolled to the study.

Inclusion Criteria

- 1. Patients age \geq 18 and < 75
- 2. Seen in primary care visit within Vanderbilt University Medical Center

PI: [name], MS

3. Eligible for statin therapy due to: 1) ASCVD 10-year risk \geq 10%, 2) Type 1 or 2 diabetes and age \geq 40, or 3) ASCVD diagnosis.

Exclusion Criteria

Patient records within the EMR indicate:

- 1. Already on statin, ezetimibe, bempedoic acid, or PCSK9 inhibitor
- 2. Last known LDL-C level < 100 mg/dL
- 3. Known to be pregnant or lactating
- 4. Palliative care
- 5. Statin allergy or adverse effect of statin
- 6. Rhabdomyolysis
- 7. Statin contraindicated due to liver disease, defined as 1) Decompensated liver disease, 2) AST or ALT >5 times the upper limit of normal, or 3) Total bilirubin > 1.5 mg/dL.
- 8. Statin contraindicated due to kidney disease, defined as 1) Dialysis or 2) Estimated glomerular filtration rate < 15 ml/min/1.73 m².
- 9. Has had coronary calcium computerized tomography
- 10. Less than 3 months since lipid panel resulted
- 11. Acute visit

Study Design

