- The analysis set will include all participants in the target population for the analysis of statin prescription placed within 24 hours (the primary endpoint), statin prescription placed within 12 months after enrollment BPA (a secondary endpoint), non-statin lipid lowering agent prescription placed within 12 months after enrollment (an exploratory endpoint), and new ASCVD event within 12 months of enrollment (an exploratory endpoint).
- For the analysis of the first LDL-C level measured during the follow-up (a secondary endpoint), statin prescription filling within 12 months of enrollment (an exploratory endpoint), and time from enrollment to statin prescription (an exploratory endpoint), the analysis set will include participants in the target population who do have the outcome measures but exclude patients whose outcomes are missing even after imputing the outcomes as described in the section, 'Handling Missing Data.'

Descriptive Analysis

General approach:

Categorical variables will be summarized using frequencies and proportions, and continuous variables will be described using means and standard deviations, as well as medians and interquartile ranges. The data also will be described graphically as needed. Missingness will be reported for each variable. No statistical comparisons between arms will be performed for these descriptive analyses.

Characteristics of the study sample:

Patient baseline demographic and clinical data as well as the provider information will be summarized overall and by intervention arm. The following variables will be described at time of enrollment:

• Patient sex (male, female, unknown)

PI: [name], MS

- Patient race (African American, Asian/Pacific Islander, Caucasian, Multiple, Native American, Other, Unknown)
- Patient self-reported ethnicity (Hispanic, Non-Hispanic, Unknown)
- Patient age (years)
- Patient comorbidities:
 - o Diabetes (Yes/No)
 - o ASCVD diagnosis (Yes/No)
 - o Congestive heart failure (Yes/No)
 - Hypertension (Yes/No)
 - o Peripheral artery disease (Yes/No)
 - o Stroke (Yes/No)
- Patient body mass index (BMI, kg/m²)
- Patient Charlson comorbidity index
- Type of patient statin therapy recommended to provider (moderate intensity, high intensity, high intensity and potential work up for LDL >= 190, low-dose statin for liver disease)
- Provider role (e.g., physician, physician assistant, resident physician, nurse practitioner)
- Prior statin prescription
- Visit type (in person or telemedicine)

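### Missing follow-up LDL-C is filled with an old value and analysed as measured, which can bias the arm difference either way and overstates precision; the adjusted model also needs a test time that untested patients lack

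*SAP*

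**What the plan says.** The second secondary endpoint in the SAP is the first LDL-C between 30 days and 12 months after the enrollment visit. The SAP expects some of these values to be missing and gives this rule: "if a prior LDL-C level is available, the outcome will be imputed using the last known LDL-C level prior to the follow-up period". Patients with no earlier value are left out. Under Analysis Dataset the LDL-C set will "exclude patients whose outcomes are missing even after imputing the outcomes as described in the section" on missing data, so filled patients stay in. The main model is an unadjusted linear regression on arm (ordinal if the values are highly skewed) with 95% confidence intervals. Neither document plans a sensitivity analysis for missing LDL-C.

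Five other provisions bear on the point:

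- **Exclusion criteria:** they remove patients with "Last known LDL-C level < 100 mg/dL" and with "Less than 3 months since lipid panel resulted".
- **Source of LDL-C (Protocol 6.4):** outcomes "such as statin prescription status and post-intervention LDL-C, are abstracted from the EMR and linked to identifiers". No study blood draw is scheduled.
- **Alert content (Protocol 7.2):** the alert lets the clinician choose "a referral to a specialist such as a lipid or gastroenterology specialist". The control arm sees no alert.
- **Intercurrent events (SAP):** "To handle intercurrent event due to death or switching providers to other institutions, a whilealive strategy will be used".
- **Adjusted LDL-C model (SAP):** the covariates include baseline LDL-C and end with "provider role, and time from enrollment to follow-up LDL-C level measurement".

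**The concern.** Unless a test happened to fall in the first 30 days, the filled value predates enrollment by at least 3 months and is at least 100 mg/dL. Two errors follow. An untested patient who starts a statin is given no response. And because entry selects on a last value of 100 or more, the filled value tends to exceed a later one even in a patient who starts nothing (regression to the mean).

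The first error pulls the arm difference toward zero. The second cancels or adds, depending on whether retesting differs by arm, and nothing in the plan makes retesting equal. The LDL-C difference could therefore be understated, overstated or falsely present.

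Filled values carry no follow-up variation. In the adjusted model they largely repeat the baseline LDL-C covariate, so the interval looks more precise than the measurements allow.

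Two rules also do not fit together. Carry-forward supplies a day-30-to-month-12 value for a patient who died before day 30, despite the while-alive strategy. And the adjusted model needs a test time that does not exist for an untested patient. That time is also a post-randomization variable.

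**Working it through.** **The plan's figures.** The only design calculation is for the primary endpoint: 3% vs 6%, two-sided 0.05, 90% power. With pooled variance, n = [1.960·√(2·0.045·0.955) + 1.282·√(0.03·0.97 + 0.06·0.94)]² / 0.03² gives 1,002 per arm, 3,006 in total, as stated. For LDL-C the documents give no SD, effect, power or missing rate, so everything below except n = 1,000 per arm is assumed.

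**Assumed inputs.** Share starting a statin: pA = 20% (alert), pC = 15% (control). Statin effect: 45 mg/dL. True difference: -(0.20 - 0.15)·45 = -2.25 mg/dL. Untested shares: us (starters) and un (non-starters). Average fall without a statin: d = 0 to 6 mg/dL. If true LDL-C has mean 125 and SD 30 with within-person SD 18, the entry floor of 100 alone gives d of about 3.8.

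**Step 1: closed form.** Tested starters fall by d + 45, tested non-starters by d, and filled patients by 0. So

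carry-forward difference = -{[pA(1-usA) - pC(1-usC)](d+45) + [(1-pA)(1-unA) - (1-pC)(1-unC)]d}

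- 40% of everyone untested: -(0.03(d+45) - 0.03d) = -1.35 at any d. 60% untested: -0.90.
- Starters 10%, others 30% untested, same in both arms: -(2.025 + 0.01d), or -2.03 to -2.09.
- Starters 10%; others 30% alert vs 50% control: -(2.025 + 0.18d), or -2.03/-2.39/-2.71/-3.11 at d = 0/2/3.8/6. This exaggerates once d exceeds 0.225/0.18 = 1.25.
- Reversed, others 50% alert vs 30% control: -(2.025 - 0.15d), or -2.03/-1.73/-1.46/-1.13.
- No true effect, 18% start in both arms, others 30% vs 50% untested: -0.82·0.20·d, or -0.33/-0.62/-0.98 at d = 2/3.8/6.

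With equal retesting by arm, the difference shrinks only if us(d+45) > un·d. At d = 3.8 that means un/us below 48.8/3.8 = 12.8, which covers most plausible cases.

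**Step 2: simulation** (1,000 per arm, 2,000 replicates, 20 imputations, simulated d = 3.77; null carry-forward row 6,000 replicates). Estimates in mg/dL, unadjusted/adjusted:

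| Retested | Carry-forward | Multiple imputation |
|---|---|---|
| 60% of all | -1.37 / -1.34 | -2.26 / -2.23 |
| 40% of all | -0.95 / -0.92 | -2.31 / -2.29 |
| Starters 90%; others 70% alert, 50% control | -2.72 / -2.69 | -2.27 / -2.25 |
| Starters 90%; others 50% alert, 70% control | -1.47 / -1.44 | -2.26 / -2.24 |
| No effect; others 70% alert, 50% control | -0.62 / -0.61 | -0.02 / 0.00 |

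In the last row carry-forward rejects in about 7% of trials unadjusted (6.6% to 7.4% across runs) and 8% to 9% adjusted (7.8% to 9.1%). With 2,000 per arm the rates are 9.1% and 11.5%. Multiple imputation rejects in 5.1% and 4.9%. With equal retesting, carry-forward stays near 5%.

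**Step 3: precision at 60% retested.**

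| | Carry-forward | Everyone measured | Multiple imputation |
|---|---|---|---|
| SE, unadjusted | 1.43 | 1.56 | 1.80 |
| SE, adjusted | 1.06 | 1.31 | 1.58 |
| Coverage, unadjusted / adjusted | 91% / 86% | – | 96% / 95% |

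**Step 4: other assumptions.** With uptake of 20% vs 10%, a 35% reduction, SDs of 25 and 15, and a true difference of about -4.6, 40% missing gives a carry-forward estimate of -2.76, with coverage of 67% unadjusted and 48% adjusted. Complete-case analysis is not a safe substitute: it was off by up to about 2 mg/dL when testing depended on statin start or arm.

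**Step 5: test time.** The SAP's rule for missing covariates expects few or none and imputes them. Applied here, it would invent a date for a test that did not happen. Dropping untested patients instead would give the adjusted and unadjusted models different populations. The numerical effect depends on test timing that the documents do not give, so it is not quantified.

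**The case against.** Several points on the other side are fair.

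- **The undercoverage is mostly bias.** A bias of 0.88 with SE 1.43 gives 90.6% coverage, and 0.91 with 1.06 gives 86.2%. The carry-forward SE matches the spread of the carry-forward estimate. This stands: the SE is right for the wrong quantity. The narrow interval is not a separate failure, but a reader would still take it as the precision of the follow-up difference.
- **Exaggeration needs a sizeable retesting gap.** The figures use 20 points. With 5 points the null error at d = 3.8 is 0.82·0.05·3.8 = 0.16 mg/dL, about a tenth of the SE. With 30% of alert non-starters untested, exaggeration at d = 3.8 needs a gap of about 6, 13 or 28 points if 10%, 20% or 40% of starters are untested. The documentary support is thin: uncontrolled retesting and an optional referral. This also stands. Shrinkage is the likelier result, and the other direction is conditional.
- **The illustration gives every starter the full effect at the first test.** Set against the planned 24-hour rates of 6% and 3%, 70% to 80% of the assumed starters would begin later, some after that test. So the true difference may not be -2.25. The mechanism does not change, and multiple imputation stayed within about 0.1 mg/dL with late or test-triggered starts.
- **The stakes are limited.** Under these inputs power is low with any method: 17% carry-forward, 25% multiple imputation, 29% with everyone measured. Deaths before day 30 should be rare. Both points bear on priority, not on whether the rule is sound.

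**Conclusion.** The concern holds. Followed as written, the SAP reports an LDL-C difference that depends on a retesting pattern the trial does not control, and nothing in the plan would reveal the error. Confidence is high for the mechanism and for the undefined test time, which follow from the text. The size cannot be determined from the documents.

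Under the assumed inputs, equal retesting by arm most often shrinks the difference, from -2.25 to -1.35 or -0.90 with 40% or 60% untested. Unequal retesting can exaggerate it or create a difference of a few tenths to about 1 mg/dL where none exists. The main risk is a wrong estimate, not lost power. One secondary endpoint is affected; the primary endpoint and the sample size are not. The SAP should be changed before LDL-C is analysed.

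**What to change.** 1. Replace carry-forward with multiple imputation of follow-up LDL-C from arm, baseline LDL-C, the listed baseline covariates, and follow-up statin prescription and fill status. Use the last two in the imputation model only. Keep carry-forward at most as a sensitivity analysis. The unadjusted main LDL-C model can stay.
2. Align this with the while-alive strategy. Impute nothing after death; leave out, and count by arm, patients who die before day 30. State whether patients who move institutions are imputed from data up to departure or left out, and use the other choice as a sensitivity analysis.
3. Add missing-not-at-random analyses that shift imputed values by arm, separately in untested starters and untested non-starters. Non-starters matter most. A 2 mg/dL shift moves the difference by 0.85·0.50·2 = 0.85 in control non-starters (50% untested) and by 0.80·0.30·2 = 0.48 in alert non-starters (30% untested), but by only 0.03 to 0.04 in starters (10% untested).
4. Report the retested share by arm and by statin start. The SAP already promises missingness per variable.
5. Remove the test-time term from the adjusted LDL-C model.

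**Cost.** SAP wording and modest programming on data already to be collected. The interval widens (unadjusted SE 1.80 instead of 1.43 at 60% retested).

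The method also relies on fill records, which the SAP allows may be missing. Suppose 25% of those prescribed never fill (true difference -0.05·0.75·45 = -1.69), with 80% of fillers and 20% of non-fillers retested:

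| Never-prescribed patients retested | Carry-forward | Imputation on prescription alone | With fill status |
|---|---|---|---|
| 60% in both arms | -1.36 | -2.07 | -1.68 |
| 70% alert, 50% control | -1.98 | -2.06 | -1.67 |

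Without fill data, imputation is therefore slightly worse than carry-forward here (errors 0.38 vs 0.33, and 0.37 vs 0.29). Fill records missing at random in 30% or 50% could be imputed without visible loss (-1.57 and -1.58, against -1.57 with full data). Fill records missing for other reasons would weaken the method.
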